### **5.4. Screen Failures**

Screen failures are defined as participants who consent to participate in the clinical study but are not subsequently randomly assigned to treatment. A minimum set of screen failure information is required to ensure transparent reporting of screen failures to meet the Consolidated Standards of Reporting Trials publishing requirements and to respond to queries from regulatory authorities. Minimum information includes date of informed consent, demography, reason(s) for screen failure, and eligibility criteria.

## **6. STUDY INTERVENTIONS**

### **6.1. Study Interventions Administered**

The term “study intervention” refers to mRNA-1011.1, mRNA-1011.2, and mRNA-1012.1, and mRNA-1010 controls (mRNA-1010, mRNA-1010.2 and mRNA-1010.3) that will be administered in this study. The vaccines to be evaluated are described in [Section 4.1](#).

All mRNAs are formulated in LNPs composed of 4 lipids and provided as a sterile liquid for injection, white-to-off white dispersion in appearance.

### **6.2. Randomization**

Randomization will be performed using an IRT system.

The Sponsor’s Biostatistics Department or designee will generate the randomized allocation schedule(s) for vaccination group assignment. Overall, approximately 700 healthy adults will be randomized in parallel into 7 treatment arms to receive either mRNA-1011.1, mRNA-1011.2, and mRNA-1012.1 candidate seasonal influenza vaccines or mRNA-1010 control (mRNA-1010, mRNA-1010.2, and mRNA-1010.3) vaccines, with approximately 100 healthy adult participants randomly assigned to each of vaccination groups 1 to 7. Different dose levels will be assessed in parallel ([Table 3](#)). Randomization will be stratified by influenza vaccination status in the previous influenza season (received or not received).

### **6.3. Preparation/Handling/Storage/Accountability**

#### **6.3.1. Preparation of Study Intervention**

The study intervention will be prepared for each participant based on the vaccination group. The study intervention (mRNA-1011.1, mRNA-1011.2, mRNA-1012.1, and mRNA-1010 controls) preparation instructions are detailed in the Pharmacy Manual.

#### **6.3.2. Study Intervention Administration**

The study intervention (mRNA-1011.1, mRNA-1011.2, mRNA-1012.1, and mRNA-1010 controls) will have a dose volume of 0.5 mL and will be administered as a single IM injection into the deltoid muscle on Day 1, with preference in the non-dominant arm.

Participants will be monitored for a minimum of 60 minutes after administration of the study intervention. Assessments will include vital sign measurements and monitoring for local or systemic reactions as shown in the SoE ([Table 1](#)).

The study site will be appropriately staffed with individuals with basic cardiopulmonary resuscitation training/certification. Either onsite resuscitation equipment and personnel or appropriate protocols for the rapid transport of a participant to a resuscitation area or facility are required.

Further instructions for the preparation and administration of mRNA-1011.1, mRNA-1011.2, mRNA-1012.1, and mRNA-1010 controls are described in the Pharmacy Manual.

### **6.3.3. Study Intervention Delivery and Receipt**

The Sponsor or designee is responsible for the following:

- Supplying the study interventions; mRNA-1011.1, mRNA-1011.2, mRNA-1012.1, and mRNA-1010 controls.
- Confirming the appropriate labeling of the study intervention for clinical study use so that it complies with the US legal requirements.

The Investigator is responsible for acknowledging receipt of the study intervention by a designated staff member at the site, which includes the following:

- Confirming that the study intervention was received in good condition.
- Confirming that the temperature during shipment from the Sponsor to the Investigator's designated storage location was appropriate.
- Confirming that the Sponsor has authorized the study intervention for use.
- Ensuring the appropriate dose level of the study intervention is properly prepared using aseptic technique.

Further description of the study intervention and corresponding instructions for the receipt, storage, preparation, administration, accountability, and destruction are described in the Pharmacy Manual.

### **6.3.4. Study Intervention Packaging and Labeling**

The study intervention will have all required labeling per regulations and will be supplied to the pharmacy in an unblinded manner.

All study interventions used in this study will be prepared, packaged, and labeled in accordance with the standard operating procedures of the Sponsor or of its designee, CFR Title 21 GMP guidelines, ICH GCP guidelines, guidelines for Quality System Regulations, and applicable regulations.

### **6.3.5. Study Intervention Storage**

All study interventions must be stored in a secure area with limited access and must be protected from moisture and light until it is prepared for administration in accordance with the instructions in the Pharmacy Manual.

### **6.3.6. Study Intervention Accountability**

The Investigator is responsible for ensuring the study intervention accountability staff maintain an accurate record of the shipment receipt, the inventory at the site, dispensing of study intervention, and the return to the Sponsor or alternative disposition of used/unused product(s) in a drug accountability log. Drug accountability will be noted by the site monitor during site visits and at the completion of the study. For further direction, refer to the Pharmacy Manual.

### **6.3.7. Study Intervention Handling and Disposal**

A site monitor will reconcile the study intervention during study conduct and at the end of the study for compliance. Once fully reconciled at the site, the study intervention can be destroyed at the investigational site or a Sponsor selected third party, as appropriate.

Study intervention may be destroyed at the study site only if permitted by local regulations and authorized by the Sponsor. A document for destruction (ie, Certificate of Destruction) must be obtained and sent to the Sponsor or designee. Refer to Pharmacy Manual for further directions.

### **6.4. Study Intervention Compliance**

All study interventions will be administered at the study site under direct observation of medically qualified study staff, and study intervention administration will be appropriately recorded (date and time) in the eCRF. Qualified staff will confirm that the participant has received the entire dose of the study intervention. If a participant does not receive the study intervention, the reason for the missed dose will be recorded. Data will be reconciled with site accountability records to assess compliance.

The study site staff are responsible for ensuring that participants comply with the allowed study visit windows. If a participant misses a visit, every effort should be made to contact the participant and complete a visit within the defined visit window specified in the SoE ([Table 1](#)). If a participant does not complete a visit within the time window, that visit will be classified as a missed visit and the participant will continue with subsequent scheduled study visits. All safety requirements of the missed visit will be captured and included in the subsequent visit.

### **6.5. Dose Modification**

No dose modifications are allowed.

### **6.6. Continued Access to Study Intervention after the End of the Study**

There will be no access to study intervention following the end of the study.

### **6.7. Prior and Concomitant Therapy**

At each visit, the study site staff should question the participant regarding any medications taken and vaccinations received and record the information as specified in [Section 6.7.1](#) and [Section 6.7.2](#).

#### **6.7.1. Prior Medications and Therapies**

Information about prior medications (including any prescription or over-the-counter medications, vaccines, or blood products) taken by the participant within the 28 days before providing informed consent (or as designated in the inclusion/exclusion requirements) will be recorded in the eCRF.

#### **6.7.2. Concomitant Medications and Vaccinations**

The following information regarding concomitant medication and vaccinations will be recorded in the eCRF:

- All nonstudy vaccinations administered within the period starting 28 days before the study intervention and through Day 181 (Month 6)/EoS.
- Any authorized or investigational COVID-19 vaccine at any time before the study intervention and through Day 181 (Month 6)/EoS.
- All concomitant medications taken through 28 days after the study intervention. Antipyretics and analgesics taken prophylactically (ie, taken in the absence of any symptoms in anticipation of an injection reaction) will be recorded as such.
- Systemic steroids ( $\geq 10$  mg/day of prednisone or equivalent), immunosuppressants, immunoglobulins, or long-acting biological therapies that affect immune responses (eg, infliximab), or blood products administered at any time during the study period after the study intervention.
- Any concomitant medications relevant to or for the treatment of a SAE, AESI, or MAAE from Day 1 through Day 181 (Month 6)/EoS.
- The participant will be asked in the eDiary if they have taken any antipyretic or analgesic medication to treat or prevent fever or pain within 7 days after the study intervention, including the day of injection. Reported antipyretic or analgesic medications should be recorded in the source document by the study site staff during the study visits after vaccination or via other participant interactions (eg, telephone calls).

Concomitant medications (including vaccinations) will be coded using the WHO Drug Global Dictionary.

It is the Investigator's responsibility to ensure that details regarding the concomitant medications are adequately recorded in the eCRF.

### **6.7.3. Concomitant Medications and Vaccines that May Lead to the Elimination of a Participant from Per-Protocol Analyses**

The use of the following concomitant medications and/or vaccines will not require withdrawal of the participant from the study but may determine a participant's evaluability in the PP analysis (Analysis sets are described in [Section 9.4.](#)):

- Any investigational or non-registered product (drug or vaccine) other than the study intervention used during the study period.
- Immunosuppressants administered chronically (more than 14 days in total) during the study period. For corticosteroids,  $\geq 10$  mg/day of prednisone or equivalent is not permitted. Inhaled, nasal, and topical steroids are allowed.
- An authorized or licensed vaccine administered within 28 days after the study vaccination.
- Immunoglobulins or long-acting biological therapies that affect immune responses (eg, infliximab) or any blood products administered during the study period.

## 7. DELAY OR DISCONTINUATION OF STUDY INTERVENTION AND PARTICIPANT DISCONTINUATION/WITHDRAWAL

### 7.1. Pause Rules

Study pause rules will be continuously monitored during the study by the Investigators and IST, as warranted. If the Investigator and/or IST request that the study be paused due to a safety concern, further study intervention will be suspended while all other planned procedures relating to safety, reactogenicity, and immunogenicity assessments will continue as described in the protocol. The Sponsor will notify the Center for Biologics Evaluation and Research within 48 hours in the event of a study pause.

#### 7.1.1. Pause Rules Based on the Occurrence of a Single Event and Adjudicated by the Data Safety Monitoring Board

The occurrence of any of the events listed in [Table 4](#), regardless of the treatment arm, will result in immediate pause of enrollment. An unscheduled safety review will be convened to assess specific data concerns and make recommendations.

**Table 4: Pause Rule Criteria, Events, and Thresholds - Single Event**

Pause Rule	Event	Number of Participants
1	Any SAE that cannot be reasonably attributed to a cause other than study vaccination	≥1
2	Any Grade 4 local or systemic solicited AR or any Grade 4 laboratory abnormality that cannot be reasonably attributed to a cause other than study vaccination a	≥1
3	Any case of myocarditis and/or pericarditis that cannot be reasonably attributed to a cause other than study vaccination	≥1

Abbreviations: AE = adverse event; AR = adverse reaction; FDA = Food and Drug Administration; SAE = serious adverse event; US = United States.

a Grading of laboratory parameters will be based on the US FDA Guidance for Industry “Toxicity Grading Scale for Healthy Adult and Adolescent Volunteers Enrolled in Preventive Vaccine Clinical Trials.” ([DHHS 2007b](#)).

#### 7.1.1.1. Pause Rules Based on the Occurrence of Events in a Proportion of Participants

The occurrence of safety events that will pause study dosing based on defined threshold levels, which are aggregate incidences relative to the number of exposed participants within a vaccination group, are summarized in [Table 5](#).

**Table 5: Pause Rule Criteria, Events, and Thresholds – Proportion of Participants**

Pause Rule	Event	Number or Percentage of Participants a
4	Any severe unsolicited nonserious AE that cannot be reasonably attributed to a cause other than the study vaccination (independent of within or not within the same system organ class)	≥2 participants per group or ≥20% of total participants b
5	Any Grade 3 local solicited AR lasting more than 48 hours that cannot be reasonably attributed to a cause other than the study vaccination, starting within the 7-day postdosing period c	≥2 participants per group or ≥20% of total participants b
6	Any Grade 3 systemic solicited AR lasting more than 48 hours (24 hours for fever) that cannot be reasonably attributed to a cause other than the study vaccination, starting within the 7-day postdosing period c	≥2 participants per group or ≥20% of total participants b

Abbreviations: AE = adverse event; AR = adverse reaction; MedDRA = Medical Dictionary for Regulatory Activities.

- a The rate of AEs/ARs will be computed based on the number of exposed participants in each treatment group. For solicited ARs, participants need to experience the same solicited AR. Unsolicited events will be counted independent of within or not within the same system organ class.
- b For the first 7 participants in each dosing group, the pause rule will be considered met if two of the first 7 participants experience AEs/ARs per footnote a. The calculation for ≥20% of participants includes the total number of participants within a dosing group who have completed a postdosing visit in the denominator. Reactogenicity e-diary data confirmed by the Investigator as being entered by the participant in error will not contribute toward a stopping rule.
- c Grading of parameters will be based on the US FDA Guidance for Industry “Toxicity Grading Scale for Healthy Adult and Adolescent Volunteers Enrolled in Preventive Vaccine Clinical Trials.” ([DHHS 2007b](#)).

If a pause is triggered in the study, each participant's study site visits will continue until EoS. If a pause affects a participant's vaccination visit, the window for that participant's vaccination visit will be suspended until the pause is lifted and vaccination can resume. Once the pause is lifted, vaccination should be reinstated as soon as possible.

If a participant is in the screening period for more than 28 days as a result of a pause, the participant may be rescreened for study eligibility (and will receive a new screening number) as long as the participant continues to provide consent to participate in the study.

## 7.2. Criteria for Delay or Withholding of Study Intervention

Body temperature must be measured at the dosing visit before administration of study intervention. The following events constitute criteria for delay of injection, and if any of these events occur at the time scheduled for dosing, the participant may be injected at a later date within the time window specified in the SoE ([Table 1](#)):

- Acute moderate or severe infection with or without fever at the time of dosing.
- Fever, defined as body temperature ≥38.0°C (100.4°F) at the time of dosing.
- Receipt of all other vaccinations within 28 days of planned Day 1.

Participants with a minor illness in the absence of fever, as assessed by the Investigator, can be administered the study intervention. Participants with a fever  $\geq 38.0^{\circ}\text{C}$  ( $100.4^{\circ}\text{F}$ ) will be contacted within the time window acceptable for participation and reevaluated for eligibility. If the Investigator determines that the participant's health on the day of administration temporarily precludes injection, the visit should be rescheduled within the allowed interval for that visit.

The Investigator, in consultation with the Sponsor's medical monitor, should withhold the study intervention if the participant meets any of the following criteria:

- Becomes pregnant.
- Develops symptoms or conditions listed in the exclusion criteria.
- Experiences a clinically significant change in clinical laboratory test results, vital sign measurements or general condition that, in the judgment of the Investigator, requires withholding of study intervention.

The reason(s) for withholding the study intervention will be recorded in the eCRF.

If a participant takes a prohibited drug therapy, the Investigator could delay the study intervention within the visit window or withhold the study intervention based on a joint decision of the Investigator and the CRO's medical monitor.

### **7.3. Participant Discontinuation/Withdrawal from the Study**

Participants who withdraw or are withdrawn from the study will not be replaced unless otherwise stated in the protocol.

A "withdrawal" from the study refers to a situation wherein a participant does not return for the final visit planned in the protocol.

Participants can withdraw consent and withdraw from the study at any time, for any reason, without prejudice to further treatment the participant may need to receive. The Investigator will request the participant to complete all study procedures pending at the time of withdrawal.

If a participant desires to withdraw from the study because of an AE, the Investigator will attempt to follow-up with the participant until the event is considered resolved or stable and will then complete the EoS section of the eCRF.

All data collected until the date of withdrawal or last contact of the participant will be used for the analysis.

Information related to the withdrawal will be documented in the eCRF. The Investigator will document whether the decision to withdraw a participant from the study was made by the participant or by the Investigator, as well as the reason for withdrawal.

Participants who are withdrawn from the study because of AEs (including SAEs, solicited ARs, or reactogenicity events) must be clearly distinguished from participants who are withdrawn for other reasons. Investigators will follow-up with participants who are withdrawn from the study as a result of an AE, SAE, solicited AR, or reactogenicity event until resolution of the event.

A participant withdrawing from the study may request destruction of any samples taken and not tested, and the Investigator must document this in the site study records.

If the participant withdraws consent for disclosure of future information, the Sponsor may retain and continue to use any data collected before such a withdrawal of consent ([Section 11.1.6](#)).

The Sponsor will continue to retain and use all research results that have already been collected for the study evaluation, unless the participant has requested destruction of these samples. All biological samples that have already been collected may be retained and analyzed at a later date (or as permitted by local regulations).

#### **7.4. Lost to Follow-up**

A participant will be considered LTFU if he or she repeatedly fails to return for scheduled visits without stating an intention to withdraw consent and is unable to be contacted by the study site. The following actions must be taken if a participant fails to return to the clinic for a required study visit:

- The site must attempt to contact the participant and reschedule the missed visit as soon as possible, counsel the participant on the importance of maintaining the assigned visit schedule and ascertain whether the participant wishes to and/or should continue in the study.
- Before a participant is deemed LTFU, the Investigator or designee must make every effort to regain contact with the participant (where possible, 3 telephone calls and, if necessary, a certified letter to the participant's last known mailing address or local equivalent methods). These contact attempts (eg, dates of telephone calls and registered letters) should be documented in the participant's medical record.
- A participant who continues to be unreachable or continues to be noncompliant with study visits or procedures will be considered to have withdrawn from the study.
- A participant should not be considered LTFU until due diligence, as described above, has been completed.

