### 8.2. Safety Assessments and Procedures

Safety assessments will include monitoring and recording of the following for each participant, according to the SoE ([Table 1](#)):

- Solicited local and systemic ARs ([Section 8.4.4](#)) that occur during the 7 days following the study intervention (ie, the day of study vaccination [Day 1] and 6 subsequent days). Solicited ARs will be recorded daily using eDiaries.
- Unsolicited AEs observed or reported within 28 days following the study intervention, with the day of study vaccination as Day 1 ([Section 8.4.2](#)).

- AEs leading to discontinuation from study participation from Day 1 through Day 181 (Month 6)/EoS or withdrawal from the study.
- MAAEs from Day 1 through Day 181 (Month 6)/EoS or withdrawal from the study ([Section 8.4.5](#)).
- AESIs from Day 1 through Day 181 (Month 6)/EoS or withdrawal from the study ([Section 8.4.6](#)).
- SAEs from Day 1 through Day 181 (Month 6)/EoS or withdrawal from the study ([Section 8.4.3](#)).
- Results of abnormal safety laboratory tests ([Section 8.2.12](#)).
- Abnormal vital sign measurements ([Section 8.2.1](#)).
- Abnormal physical examination findings ([Section 8.2.1](#)).
- Details of all pregnancies in female participants will be collected from Day 1 through Day 181 (Month 6)/EoS ([Section 8.2.2](#)).

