6.1. General Considerations

All analyses will be conducted using SAS Version 9.4 or higher.

All analyses will be performed by treatment arm, unless otherwise specified.

Continuous variables will be summarized using the following descriptive summary statistics: the number of participants (n), mean, standard deviation (SD), median, minimum, and maximum. The mean and median will be presented to one decimal place more than the minimum and maximum and the SD will be presented to two decimal places more than the minimum and maximum.

Categorical variables will be summarized using frequencies and percentages. Percentages will be presented to one decimal place. When count data are presented, the percentage will be suppressed when the count is zero in order to draw attention to the non-zero counts. The denominator for all percentages will be the number of participants in the vaccination group within the analysis set of interest, unless otherwise specified.

Confidence interval (CI) will be presented to one more decimal place than the point estimate. **Baseline value**, unless otherwise specified, is defined as the most recent non-missing measurement (scheduled or unscheduled) collected before the dose of the study vaccination. For immunogenicity tests and nasopharyngeal (NP) swab tests, baseline is defined as the most recent non-missing result (scheduled or unscheduled) collected on or before the Day 1 injection date (or date/time if available).

Visit window rules for protocol-defined visits are provided in [Appendix A](#).

Unscheduled visits will be included in the analyses as follows:

- Mapped to the scheduled visit windows per specified visit windowing rules.
- Included in the derivation of baseline/last on-treatment measurements.

- Included in the derivation of maximum/minimum on-treatment values and maximum/minimum change from baseline values for safety analyses.
- Presented in individual participant data listings as appropriate.

Analysis periods to be used for safety analyses:

- Overall period: starts from the day of vaccination (Day 1) and continues through the earliest date of (study completion, discontinuation from the study, or death).
- 7 days following vaccination: starts from the day of vaccination and 6 subsequent days, or up to the study discontinuation or death, whichever comes earlier. This analysis period will be used for solicited local and systemic ARs that occur during this time.

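### Section 7.4 deems a reachable but persistently noncompliant participant withdrawn, which ends active safety collection before Day 181, and sections 6.4, 7.3 and 7.4 do not say which rule governs

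*Protocol*

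**What the plan says.** **Protocol 7.4.** The opening sentence defines lost to follow-up by two joint conditions: repeated failure to return, and that the person "is unable to be contacted by the study site". When someone fails to return for a clinic visit, the site must make contact, reschedule, counsel, and "ascertain whether the participant wishes to and/or should continue in the study". The third bullet then treats as withdrawn anyone who remains unreachable, or who "continues to be noncompliant with study visits or procedures will be considered to have withdrawn from the study". It gives no number of missed visits.

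**Protocol 6.4.** For a visit missed outside its window, "that visit will be classified as a missed visit and the participant will continue with subsequent scheduled study visits". It adds: "All safety requirements of the missed visit will be captured and included in the subsequent visit". There is no upper limit on missed visits.

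**Protocol 7.3.** Withdrawal is defined differently, as not returning for the final planned visit. Data up to withdrawal or last contact are analysed. Participants withdrawn because of an AE are followed until that event resolves.

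**What withdrawal ends.** Protocol 8.2 collects "SAEs from Day 1 through Day 181 (Month 6)/EoS or withdrawal from the study", with the same limit for MAAEs, AESIs and AEs leading to discontinuation. Section 8.2.7 stops MAAE, SAE and AESI collection at the end of participation. The overall safety period in SAP 6.1 "continues through the earliest date of (study completion, discontinuation from the study, or death", whichever comes first. SAP 6.4.2 bases AE percentages on the whole Safety Set.

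**The concern.** The third bullet of 7.4 is wider than the lost-to-follow-up definition at the head of the same section. Read as written, it ends safety follow-up for a person who can be reached and still consents. Nothing in the design requires that. The vaccine is a single dose given on Day 1, so long-term safety follow-up does not depend on attendance for further dosing, and most scheduled contacts after Day 29 are telephone calls that exist to collect these events.

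The events at stake are the four primary endpoints that run from Day 1 to Day 181. Events after a deemed withdrawal are not actively sought, yet the person remains in the denominator and counts as event-free for the unobserved period. Because no section says when one rule gives way to another, two sites could handle the same participant differently. If people who stop attending differ in their adverse experience, or if attendance differs by arm in this open-label study, the loss would be selective.

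**Working it through.** **1. The rules side by side, for a reachable, consenting participant who misses Day 8 and Day 29**

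| Section | Trigger | Result |
|---|---|---|
| 6.4 | a visit missed outside its window | stays in, later visits continue |
| 7.4, opening | repeated missed visits and no contact possible | not lost to follow-up, because reachable |
| 7.4, third bullet | noncompliance continues after contact and counselling | deemed withdrawn |
| 7.3 | does not return for the final visit | not yet determined |

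Sections 6.4 and 7.4 can be read in sequence, as an escalation. What is missing is the point at which the first gives way to the second.

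**2. Who is affected.** The 7.4 actions start when a participant fails to return to the clinic. Table 1 of the protocol has three post-dose clinic visits: Days 8, 29 and 181. A Day 181 absence comes when follow-up is ending anyway, so the clause matters mainly after missed Day 8 and Day 29 visits.

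**3. What could still be collected.** After Day 29, five scheduled contacts remain: calls on Days 57, 91, 121 and 151, and the Day 181 clinic visit. Four of the five are calls. Days 30 to 181 are 181 − 29 = 152 days, and 152/181 = 84.0% of follow-up.

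**4. The plan's own figure.** Table 8 of the protocol uses n = 100 per group. P(at least one event) = 1 − (1 − p)^100:
- p = 1%: 63.4%
- p = 2%: 86.7%
- p = 3%: 95.2%
- p = 4%: 98.3%

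All four match the table.

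**5. Effect of deemed withdrawal.** The documents give no withdrawal rate. Assume k of 100 participants per arm are deemed withdrawn at Day 29, with events spread evenly over 181 days.

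Share of the arm's planned follow-up lost = (k/100) × 152/181.

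P(at least one event) = 1 − (1 − p)^(100 − k) × (1 − p × 29/181)^k.

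For p = 2%, p × 29/181 = 0.0032. At k = 5: 1 − 0.98^95 × 0.9968^5 = 0.856.

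| k per 100 (assumed) | Follow-up lost | Chance, followed to Day 29 | Chance, no follow-up at all (1 − 0.98^(100 − k)) |
|---|---|---|---|
| 0 | 0% | 86.7% | 86.7% |
| 2 | 1.7% | 86.3% | 86.2% |
| 5 | 4.2% | 85.6% | 85.3% |
| 10 | 8.4% | 84.3% | 83.8% |

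The fall is about 1.1 points at k = 5 and 2.4 points at k = 10. Even with no follow-up contributed, it is about 2.9 points at k = 10. These figures treat loss as unrelated to events and say nothing about bias.

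**The case against.** The strongest reply is that the clause is the last step of an escalation, that few participants would reach it, and that safeguards already exist. Much of this stands.

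- A reader might infer that safety data are discarded. The documents do not support that: section 7.3 uses everything collected up to withdrawal or last contact. What is lost is later information that is never collected.
- A reader might infer that 6.4 and 7.4 flatly contradict each other. They do not. Section 6.4 deals with a missed visit, and 7.4 with noncompliance that persists after contact and counselling. The fault is an unstated boundary.
- A reader might infer that anyone who attends but declines a blood draw or skips the diary is withdrawn. The bullet does mention procedures, but the list it belongs to starts with a missed clinic visit, so this stretches the text.
- A reader might infer biased arm comparisons. The documents give no withdrawal rate and no evidence that noncompliance relates to adverse events or to arm. Section 4.2 argues that preference between arms should be minimal, with one platform, a narrow dose range and no placebo. No hypothesis is tested, and the primary safety analysis period in SAP 6.1 is 28 days unless stated otherwise.

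The safeguards do not close the gap. Follow-up after an AE-related withdrawal concerns that event, not new ones. Section 8.2.10 covers only SAEs that the investigator happens to learn of after discharge and considers reasonably related, whereas the primary endpoints count events regardless of relatedness. The 28-day emphasis does not remove the Day 181 endpoints, which SAP 6.4.2 also summarises to the end of the study. Counting the unobserved period as event-free is common to any dropout. The difference here is that the protocol itself creates the dropout while the participant can still be reached.

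**Conclusion.** The point holds in limited form. Section 7.4 ends active safety collection for reachable participants who have not withdrawn consent, and sections 6.4, 7.3 and 7.4 leave undefined when that happens. Four primary endpoints with a Day 181 horizon are affected.

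The expected numerical effect is small: 86.7% to about 85.6% for a 2% event at an assumed 5% withdrawn, and 86.3% to 84.3% over an assumed 2% to 10%. These figures rest on withdrawal at Day 29, an even spread of events over follow-up, and loss unrelated to events. Selective loss is a possible risk that the documents neither quantify nor demonstrate. This is an inexpensive improvement to safety ascertainment. It is not a flaw that undermines the trial.

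**What to change.** - **Section 7.4:** remove continued noncompliance with visits or procedures as a ground for deemed withdrawal, so that the third bullet applies only to participants who stay unreachable after the listed contact attempts.
- **Follow-up:** state that reachable participants who have not withdrawn consent remain in the scheduled telephone safety follow-up, with the final safety contact at Day 181 by telephone if they do not attend.
- **Section 6.4:** cross-refer to this rule, and record missed visits or procedures as protocol deviations.
- **Section 7.3:** reconcile the definition of withdrawal, so that missing the final clinic visit does not by itself make a participant withdrawn when the Day 181 safety contact was made by telephone. Changing 7.4 alone would leave this conflict. Consent withdrawal and documented withdrawal by the investigator stay as they are.

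The cost is a clause removed and a few sentences added. The calls to Day 151 are already scheduled, and sites would keep calling a few more participants, with an occasional telephone contact in place of the Day 181 visit.
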